Research question: does an enhanced diagnostic workup for patients about to start empiric tuberculosis treatment in Lusaka, Zambia, lead to alternative diagnoses and improved patient outcomes after six months?

Primary objective: to determine in what proportion of patients who are about to start empiric tuberculosis treatment, an alternative diagnosis can be made through the use of a concise additional workup by an experienced pulmonary physician, including review of available data, as well as additional laboratory, functional, and imaging investigations

Secondary objectives: to determine whether establishing and treating alternative diagnoses in patients who were about to start empiric tuberculosis treatment leads to improved quality of life and survival after six months

In- and exclusion criteria: All adult patients who have a negative initial GeneXpert MTB/RIF test on sputum, but are about to start standard first-line treatment for suspected pulmonary tuberculosis on clinical grounds (i.e. empiric tuberculosis treatment), at four first-level Hospitals in Lusaka, Zambia. Patients will be excluded if they are inpatients (due to suspected tuberculosis).

Number of eligible patients per year: Estimated 410 eligible patients per year in Chawama (450 clinically diagnosed pulmonary tuberculosis patients at Chawama first-level hospital in 2023, including children). The total population at Chawama first-level hospital in 2023 included 5361 presumptive tuberculosis cases, of whom 5270 had GeneXpert MTB/RIF testing done, and of whom 426 had a positive result from GeneXpert MTB/RIF. There is a discrepancy with the number of bacteriologically confirmed tuberculosis cases, which is reported at 663 for the year. The reason for this is not entirely clear, but might be due to additional testing being performed at different facilities, and the use of other tests for diagnosing tuberculosis, such as lipoarabinomannan assay and acid-fast bacilli smear. Interestingly, the percentage of patients who had a tuberculosis relapse was higher in patients being treated empirically than in patients with bacteriologically confirmed tuberculosis (107 out of 450 (24%) versus 107 out of 663 (16%)).

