Treatment outcomes for 2022 are as follows: 618 bacteriologically confirmed new cases of which 523 were cured (85%), 29 completed treatment, 36 died (6%), 3 failed treatment, 24 were lost to follow up, and 3 were not evaluated; 123 bacteriologically confirmed tuberculosis relapses of which 115 were

cured (93%), 5 died (4%), 2 were lost to follow up, and 1 was not evaluated; 352 clinically diagnosed new cases of which 308 completed treatment (88%), 35 died (10%), 1 failed treatment, 7 were lost to follow up, and 1 was not evaluated; 156 clinically diagnosed tuberculosis relapses of which 143 completed treatment (92%), 9 died (6%), and 3 were lost to follow up.

The other first-level hospitals had somewhat lower numbers of patients in 2023.

Intervention: All included patients will undergo the study intervention. Participants will be included from the tuberculosis clinic at first-level hospitals. They will be reviewed by one of the study physicians prior to initiating empiric tuberculosis treatment. A full history and physical examination will be taken and available results will be reviewed (laboratory results, sputum results, and chest X-ray). Depending on the results, appropriate measures will be taken there, including possible treatment with antibiotics or a wait-and-see approach for suspected viral infections. If further diagnostics are deemed to be indicated, a patient will be referred to the pulmonology clinic at University Teaching Hospital in Lusaka, Zambia. There, appropriate additional diagnostics will be requested, including additional blood tests (such as aspergillus serology), repeat chest X-ray, spirometry, CT-scan of the chest (if no other clear clinical diagnosis), bronchoscopy (if indicated based on CT-scan) and sputum and/or bronchial washing bacterial and mycobacterial cultures. The empiric treatment will be withheld initially if the study investigator thinks that an alternative diagnosis is more likely, while awaiting the additional investigations. If the study investigator thinks it is in the interest of the patient, then empiric tuberculosis treatment will be initiated while awaiting the results for the additional investigations. When a final diagnosis is made, appropriate treatment decisions will be made. If a clear diagnosis cannot be made locally, patients will be discussed in a multidisciplinary team meeting between St. Antonius Hospital and University Teaching Hospital.

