Statistical analysis: Descriptive statistics will be used to describe percentage of alternative diagnoses, as well as percentage of patients that has quality of life scores indicating they are not satisfied or very dissatisfied, the percentage of patients who received tuberculosis treatment and the percentage of patients that had side effects attributed to tuberculosis treatment. Paired analyses will be used to compare quality of life at baseline and during follow up. Multivariate regression analyses will be used to identify what factors associate with quality of life and survival. We will use per-protocol analysis methods for the primary analyses, with intention-to-treat analyses as a secondary tool. We will use a historic control group of patients who underwent empiric TB treatment at the study sites in the year prior to the study as a comparison for survival. Additionally, as data for the tuberculosis clinic are collected in a standard fashion, it will be able to compare the number of patients being referred to the clinic, the number of patients receiving treatment for bacteriologically confirmed tuberculosis, and the number of patients receiving empiric tuberculosis treatment, as well as treatment outcome data, between the study period and the period prior to and after the study.

Burden and risks for participants: The burden for the participants consists of having to travel to University Teaching Hospital (4.2 km – 10.6 km distance) for review and potential additional investigations that cannot be done on the same day (CT-scan and bronchoscopy). The additional investigations might necessitate venepuncture (slightly painful, low risk of hematoma or bleeding), chest X-ray (low dose radiation (0.1mSv)), spirometry (low risk of feeling uncomfortable), and

potentially CT-scan of the chest (medium dose radiation (6.1 mSv)), and bronchoscopy (discomfort for most patients, risk of serious complications (e.g. bleeding, pulmonary oedema, pneumothorax) ca. 1%). It needs to be emphasized that these investigations would be considered as the standard-of-care in a high-resource setting, and, in that sense, are not actually an additional burden at all.

Study duration: 16 months

Start date: 1/12/2024

Final inclusion: 31/12/2025

End date: 30/06/2026

Dissemination plan:

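### The before/during/after clinic comparison is planned in raw patient numbers with no denominator, so a change in empiric treatment cannot be separated from a change in clinic volume

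*Combined protocol and SAP*

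**What the plan says.** The last sentence of the Statistical analysis section uses data that the tuberculosis clinics already collect. It proposes to set referrals side by side across periods, together with "the number of patients receiving treatment for bacteriologically confirmed tuberculosis, and the number of patients receiving empiric tuberculosis treatment, as well as treatment outcome data". The periods are that of the study itself and those on either side of it. The sentence gives no proportion, rate, denominator, period length or statistical test for this comparison. In the same section, tuberculosis treatment and its side effects among participants are to be reported as percentages.

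The only clinic totals for more than one year are Chawama's. Number of eligible patients per year reports "450 clinically diagnosed pulmonary tuberculosis patients at Chawama first-level hospital in 2023, including children" and 663 bacteriologically confirmed cases. The paragraph on 2022 treatment outcomes gives 352 clinically diagnosed new cases and "156 clinically diagnosed tuberculosis relapses of which 143 completed treatment (92%), 9 died (6%), and 3 were lost to follow up", with 618 new and 123 relapsed confirmed cases. The protocol does not compare the two years.

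**The concern.** The number of patients treated empirically is the product of two things: how many patients come through the clinic, and how often a clinician treats without confirmation. Only the second bears on the work-up. With counts alone, an ordinary fall in attendance could be read as treatment avoided, and an ordinary rise could hide a real reduction. Equal or annualised periods do not cure this, because volume can change between two full years.

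This is the plan's only clinic-level before/after view of empiric treatment, and the Dissemination plan intends to share results with the national tuberculosis programme. A sentence such as 'empiric treatment fell by a tenth during the study' would be easy to quote and hard to interpret.

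**Working it through.** The plan states no figure for a year-on-year change, so there is none to reproduce. The check builds one from the protocol's Chawama totals.

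**Counts and share**

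| | 2022 | 2023 | Change |
|---|---|---|---|
| Empiric | 352 + 156 = 508 | 450 | -58/508 = -11.4% |
| Confirmed | 618 + 123 = 741 | 663 | -78/741 = -10.5% |
| All treated | 1,249 | 1,113 | -136/1,249 = -10.9% |
| Empiric share | 508/1,249 = 40.7% | 450/1,113 = 40.4% | -0.2 points |

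- Count comparison, empiric: z = (508 - 450)/√(508 + 450) = 1.87, p = 0.061. The ratio is 0.886, with a Poisson 95% interval of 0.780 to 1.006.
- Share comparison: the 95% interval for the difference is -4.2 to +3.7 points, chi-square p = 0.91.

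On these figures the count moved by about a tenth and the share hardly moved.

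**Are the two years comparable?** The 2023 empiric figure is labelled pulmonary and includes children. The 2022 figures are treatment-outcome cohorts with no such label. Assume that 8% of the 1,249 cases in 2022 were extrapulmonary (the complement of the national 92% in the Background):

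- Spread evenly: 508 × 0.92 = 467, and 450/467.4 - 1 = -3.7%.
- All among the clinically diagnosed: 508 - 0.08 × 1,249 = 408, and 450/408.1 - 1 = +10%. The share would then also move, from 408/1,149 = 35.5% to 40.4% (p = 0.016).

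**How large an effect could the study produce?** The Background suggests that 60-80% of empirically treated patients may be treated inappropriately. If that many of 300 participants go untreated, 180-240 treatments are avoided. Chawama's 410 eligible patients a year over 13 months of inclusion gives 410 × 13/12 = 444. Assume that each of the other three hospitals has 50-90% of Chawama's volume (the protocol says only that their numbers were somewhat lower). The multiplier is then 1 + 3 × 0.5 = 2.5 to 1 + 3 × 0.9 = 3.7, or about 1,110 to 1,640 eligible patients. The effect would be 180/1,640 = 11% to 240/1,110 = 22%, similar in size to the possible background change.

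**Illustration with an ordinary two-sided 5% Poisson count comparison** (200,000 simulated runs; means 450 and 663 times the multiplier; both counts scaled by the same volume change)

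| Scenario | Multiplier | Count | Share |
|---|---|---|---|
| No effect, volume -11.4% | 1 | 42% | 5% |
| No effect, volume -11.4% | 2.5 | 80% | 5% |
| No effect, volume -11.4% | 3.7 | 92% | 5% |
| 210 avoided, volume stable | 3.7 | 96% | 84% |
| 210 avoided, volume +11.4% | 2.5 | 42% | 92% |
| 210 avoided, volume +11.4% | 3.7 | 6% | 77% |

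The entries are the percentage of runs in which a difference is declared. A hand check of the third row: the means are 1,665 and 1,475, z = 190/√3,140 = 3.39, and P(Z > 1.96 - 3.39) = 92%.

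**Period length** adds a separate distortion: 13 months of inclusion against a 12-month year gives 13/12 - 1 = +8% at a constant rate.

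**The case against.** The strongest reply is that the plan tests nothing here. The sentence notes what routine data make possible. It sets no hypothesis or significance level, and these clinic totals are not among the listed outcomes. That stands. A reader might infer from the table above that the plan carries a 42-92% false-positive rate, but those rates belong to a count test assumed for illustration. The share's 5% also holds by construction, because both counts were scaled together.

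A reader might also infer that the study cannot measure avoided treatment. It can. Participants enrol only after a clinician has decided to treat empirically, and the number then treated is a secondary outcome reported as a percentage. Clinic volume does not affect that figure.

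Nor is volume ignored altogether. Referrals and confirmed cases are listed beside the empiric count, so a careful reader could see all three move together. What is missing is a ratio fixed in advance.

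It is tempting to say that the protocol's own figures prove an 11% background fall. They do not: the case definitions may differ, there are two years at one hospital, and the interval for the ratio just includes 1. Using the 107 relapses reported in each group for 2023, empiric new cases went from 352 to 343 (-2.6%) and empiric relapses from 156 to 107 (-31%). Confirmed new cases went from 618 to 556 (-10.0%) and confirmed relapses from 123 to 107 (-13%). The share rose among new cases (36.3% to 38.2%) and fell among relapses (55.9% to 50.0%), so the flat overall share is a net of opposite movements and not a clean common change in volume.

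The share has its own weaknesses. It shifts if case definitions differ, and its denominator uses the 663 confirmed cases, which the protocol cannot fully reconcile with 426 GeneXpert positives.

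These points reduce the weight of the concern. They do not make a change in the raw empiric count attributable to the work-up.

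**Conclusion.** The point holds in a limited form. The supplementary clinic comparison is specified in numbers without a denominator, so a change in the number treated empirically mixes volume with treatment practice. If the Chawama years are comparable, the count fell 11.4% with no study running while the share stayed near 40.5%. Under the 8% extrapulmonary assumption the change in the count lies between about -4% and +10%. Either way, movements of this order are close to the 11-22% that the study might plausibly produce under the stated volume assumptions.

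The documents do not support a claim of an invalid test, an established 11% decline, or a threat to the primary outcome. This is a modest but worthwhile correction to an additional analysis.

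**What to change.** In the Statistical analysis section, restate the clinic-level comparison of empiric treatment as proportions, by hospital and over matching calendar periods:

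1. empirically treated / (empirically treated + bacteriologically confirmed);
2. empirically treated per patient referred, or per presumptive case (Chawama 2023: 450/5,361 = 8.4%; no 2022 counterpart is given).

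Apply the same case definition (pulmonary or all sites, adults or all ages) in every period. Show participants confirmed only through the study's additional testing separately, because such confirmations move patients from the empiric to the confirmed group and lower the share without any treatment being avoided. Keep the raw numbers as description, and do not attribute their change to the work-up.

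The cost is one or two sentences; the counts are already collected routinely, and no extra patients are needed. When volume is stable the share has somewhat less power than the raw count (about 84% versus 96% at the largest assumed volume), and it must be read beside the confirmed count.

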For example, in Zambia, there were an estimated 40000 new tuberculosis cases in 2020 (with 92% pulmonary tuberculosis), 100% of whom were tested with GeneXpert MTB/RIF (or other rapid molecular diagnostics). However, only 51% of all patients who were treated for pulmonary tuberculosis were bacteriologically confirmed.¹ This is not consistent with the supposed 85% sensitivity of the GeneXpert MTB/RIF test. This might mean that a significant proportion of patients, perhaps in the order of 30-40% of all patients, and 60-80% of all empirically treated patients, receives tuberculosis treatment inappropriately. Standard tuberculosis treatment can be burdensome, as the usual treatment duration is 6 months, and 5-10% of patients are estimated to experience serious side effects.² In some cases, a self-limiting condition such as a viral respiratory tract infection might be the underlying diagnosis, which would not need to be followed up for six months. More importantly, empiric tuberculosis treatment can delay the diagnosis of another severe underlying condition such as malignancy, pulmonary aspergillosis, or interstitial lung disease. It has been shown that mortality is higher in patients that are empirically treated for tuberculosis, and this may be in part to missed other diagnoses.¹²

Over the past years, the departments of pulmonology and radiology from St. Antonius Hospital have been holding bimonthly videoconferences with the department of pulmonology at University

Teaching Hospital in Lusaka, Zambia. We have mainly discussed patients with suspected interstitial lung disease. Our experience has taught us that interstitial lung diseases, which have barely been reported in Sub-Saharan Africa, can indeed be identified when you look well enough, and that these patients have oftentimes received inappropriate empiric tuberculosis treatment prior to the diagnosis of interstitial lung disease.^{26,27}

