There are several previous studies into alternative diagnoses in patients who were empirically treated for tuberculosis, but high-quality evidence is lacking. The only prospective study was done in Tanzania, and included 36 patients. Of these patients, 23 completed all additional investigations, and only 2 of these patients (6%) were confirmed to have tuberculosis. The other patients were diagnosed with pneumonia, bronchiectasis, interstitial lung disease, non-tuberculous pleural disease, malignancy, and chronic pulmonary aspergillosis.¹⁶ A retrospective study in Pakistan found that 45% of 61 patients who received empiric treatment later were found to have an alternative diagnosis, including malignancies, heart failure, chronic pulmonary aspergillosis, and bronchiectasis.¹⁷ In another study by the same authors, it was found that over a third of patients with allergic bronchopulmonary aspergillosis in a Pakistani tertiary care hospital, had initially been misdiagnosed as tuberculosis.¹⁸ In a study from Nigeria, it was found that a significant proportion of patients that were re-treated for tuberculosis, and had been classified as treatment failures, actually had chronic pulmonary aspergillosis.¹⁹ What complicates matters, is that pulmonary aspergillosis is frequently seen as a late complication of cavitary tuberculosis, even if the latter has been adequately treated.²⁰ A recent systematic review highlighted 80 cases in which various types of pulmonary fungal infections were initially misdiagnosed as tuberculosis.²¹ Furthermore, a study from South-Africa found that almost all patients who were treated for lymphoma at a tertiary level hospital, had received empiric tuberculosis treatment in the year prior.²² A study from Uganda found a lower, but still significant rate of 30% misdiagnosis of tuberculosis in patients with HIV-associated lymphoma.²³ A study from Malawi in a general oncology department found a misdiagnosis as tuberculosis in 1% of all referred patients.²⁴

Interestingly, in another study from Uganda, it was found that 88% of 162 patients who received a course of broad-spectrum antibiotics instead of empiric tuberculosis treatment, showed clinical improvement and 4% were treated for an alternative respiratory disease.²⁵

Type of research: prospective intervention study

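### Register treatment outcomes in the study period are subject to selection by the work-up itself, and the plan defines no common denominator for comparing them with other periods

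*Combined protocol and SAP*

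**What the plan says.** The last part of the Statistical analysis section describes a supplementary use of routinely collected tuberculosis-clinic data. The counts to be compared are referrals, treatments for confirmed disease and "the number of patients receiving empiric tuberculosis treatment". Outcomes are to be compared too: "as well as treatment outcome data, between the study period and the period prior to and after the study". No denominator is given for the outcome data. The 2022 outcomes under Number of eligible patients per year are reported by treated group: confirmed or clinically diagnosed, new or relapse.

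Under Methods, patients are approached once the clinician has decided on empiric treatment. The Intervention section then states: "They will be reviewed by one of the study physicians prior to initiating empiric tuberculosis treatment". It continues: "The empiric treatment will be withheld initially if the study investigator thinks that an alternative diagnosis is more likely". The additional investigations include "sputum and/or bronchial washing bacterial and mycobacterial cultures". Treatment may also be started while results are awaited, if the investigator judges this to be in the patient's interest.

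The Background conjectures that perhaps "60-80% of all empirically treated patients, receives tuberculosis treatment inappropriately". It expects the alternative diagnoses to range from self-limiting viral infection to malignancy. It also says that "mortality is higher in patients that are empirically treated for tuberculosis, and this may be in part to missed other diagnoses".

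The documents give no common denominator, adjustment or caveat for a changed case mix in the register comparison.

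**The concern.** In the year before the study, the empirically treated group holds everyone the clinician chose to treat. During the study, some patients of the same kind never enter that group because the study physician withholds treatment, and others are reclassified as confirmed. The intervention therefore selects the group whose outcomes are compared.

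The selection is neutral only if the patients removed have the same mortality as those who remain. The Background gives reasons to expect otherwise, in both directions. Removing self-limiting illness raises mortality among those left, and removing malignancy lowers it.

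Two consequences follow. A change in register mortality could be read as benefit or harm when no patient's outcome has changed. A participant who dies after treatment was withheld is also missing from the treatment outcomes, so the comparison cannot see harm in the patients whose management the study changes most.

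The counts are not affected in this way, since a fall in empiric treatments is the intended effect.

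**Working it through.** The plan gives no figure for this comparison, so the working first confirms its register mortality and then asks how far selection alone could move it.

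**Register baseline (Chawama, 2022).** Clinically diagnosed new cases: 35/352 = 9.9% (plan: 10%). Relapses: 9/156 = 5.8% (plan: 6%). Pooled: P = 44/508 = 8.7%.

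**Coverage c, the share of eligible patients enrolled.** The plan gives 300 participants, 410 eligible a year at Chawama, and somewhat lower patient numbers at the other three sites. The inclusion dates span 13 months. The volume at the other sites is an assumption, 200 to 400 a year each.
- 200 each: (410 + 600) × 13/12 = 1,094, so c = 300/1,094 = 27%.
- 400 each: (410 + 1,200) × 13/12 = 1,744, so c = 300/1,744 = 17%.
- All 300 from Chawama: 410 × 13/12 = 444, so c = 300/444 = 68%.

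**Calculation 1: mixture with no true effect on anyone.** Let a be the share with an alternative diagnosis. The range 45% to 80% runs from the retrospective series in the Literature review ("45% of 61 patients who received empiric treatment later were found to have an alternative diagnosis") to the top of the Background's conjecture. Let R be mortality with an alternative diagnosis divided by mortality with tuberculosis. R is an assumption, 0.5 to 2. All participants with an alternative diagnosis are taken to leave the treated group.
- Tuberculosis mortality: m = P / (1 − a + aR).
- Register mortality during the study: [(1 − a)m + a(1 − c)Rm] / (1 − ac).
- Example with P = 8.66%, a = 0.60, R = 0.5, c = 0.274: m = 8.66/0.70 = 12.37%. Register mortality = (0.40 × 12.37 + 0.60 × 0.726 × 6.19) / (1 − 0.164) = 9.15%, a shift of +0.5 points.

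| Coverage | R = 0.5 | R = 1 | R = 2 |
|---|---|---|---|
| 17–27% (pooled, four sites) | 8.9–9.2% | 8.7% | 8.2–8.5% |
| 68% (all from Chawama) | 10.0–10.4% | 8.7% | 7.2–7.5% |
| 100% (a fully enrolled site) | 11.2–14.4% | 8.7% | 4.8–6.0% |

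The pooled shift is about 0.2 to 0.5 points either way. From a baseline of 10%, the plan's planning figure, it is about 0.2 to 0.6.

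**Calculation 2: wider contrast in mortality.** Coverage of 17–27% times 60–80% leaving gives 10–22% of the group removed; take r = 12% to 20%. Let q be mortality among those removed, assumed at 1% to 14%. Residual mortality = (P − rq)/(1 − r).
- r = 0.20, q = 1%: (8.66 − 0.20)/0.80 = 10.6%, a shift of +1.9 points.
- r = 0.12, q = 2%: (8.66 − 0.24)/0.88 = 9.6%, a shift of +0.9 points.
- r = 0.12, q = 12%: (8.66 − 1.44)/0.88 = 8.2%, a shift of −0.5 points.
- r = 0.20, q = 14%: (8.66 − 2.80)/0.80 = 7.3%, a shift of −1.3 points.
- Any r with q = P: no shift.

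Together the two calculations give roughly 0.2 to 2 points for the pooled comparison.

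**The case against.** The strongest reply is that this is optional context. The text says only that the data can be compared. It names no test or estimand, and register outcomes are neither a primary nor a secondary outcome. Survival has its own analysis, enrolled patients against historic controls, and the intention-to-treat version of that keeps participants with alternative diagnoses. This stands, and it limits the consequence to interpretation.

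A second reply is that the outcome data are not expressly restricted to empirically treated patients. If all treated patients are pooled, movement from empiric to confirmed no longer matters and the effect is diluted. Chawama's 2022 register mortality was (41 + 44)/(741 + 508) = 6.8%, and the inputs of Calculation 2 move it only to 6.2–7.3%. This stands in part: untreated participants still drop out of the pooled total.

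A third reply is that the shift may be hidden by sampling error. With 1,010 to 1,610 patients per period and 8.7% mortality, the 95% half-width of a difference, 1.96 × √(2 × 0.0866 × 0.9134/n), is about 1.9 to 2.5 points. That is fair on detectability, but it does not make the contrast interpretable.

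A reader might go further and infer that the artefact rivals the 5-point difference in the Sample size calculation. The documents do not support this for the pooled data. The 5 points belong to the comparison with historic controls. Taking 60% of the treated group as removed would give 18.7–20.2% at q = 1–2%, or 0.7–3.7% at q = 12–14%, but that needs near-complete enrolment at a site. Even with all 300 from Chawama, removal is at most 0.68 × 0.80 = 54%. A mostly tuberculosis remainder at 0.7% or 20% also fits poorly with 41/741 = 5.5% mortality in confirmed cases. The 60–80% is moreover a conjecture about inappropriate treatment, not a rate of leaving the register, since some participants start treatment while results are awaited.

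**Conclusion.** The point holds for contrasts that involve the study period. Followed as written, the plan compares outcomes between groups that the intervention has made different, and the resulting shift in mortality can go either way with no change for any patient.

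The size is uncertain. It is probably about 0.2 to 2 percentage points pooled over four sites, and larger at a site where most eligible patients enrol. It is zero only if removed and remaining patients have equal mortality. The range rests on assumptions that the documents do not supply: 200 to 400 eligible patients a year at each other site, the mortality of removed patients relative to the rest, and the share of participants who leave the treated group.

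Two broader conclusions might be inferred but are not supported. Before versus after is not biased by this route unless the changed practice persists after the study. The primary outcome and the intention-to-treat survival comparison with historic controls are not affected by this mechanism. The point deserves a change of wording before analysis because the remedy is cheap and a change in register mortality would be easy to misread.

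**What to change.** - For mortality, define the study-period group as all adults for whom the clinician decided on empiric treatment. That means register patients plus participants whose treatment was withheld or who were reclassified, with their six-month survival linked in from the study database. Patients who decline the study and start treatment are already in the register.
- Do not compare treatment completion or failure among the treated across periods as an effect of the work-up. These outcomes are undefined for untreated patients, so linkage cannot repair them.
- If linkage is not possible, limit the period comparison to counts of referrals, confirmed treatments and empiric treatments.
- State that the before-versus-after contrast carries the same caution if the changed practice continues after the study.

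The cost is one linkage of the study database to the clinic register, a few sentences in the Statistical analysis section, and a narrower descriptive comparison. Six-month survival is already collected, so no new patients or procedures are needed.
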